7.1.2. Serious Adverse Events (SAE)

According to the *South African Good Clinical Practice Guidelines* (Department of Health; 2006), SAE is defined as “an event that is associated with death, admission to

hospital, prolongation of a hospital stays, persistent or significant disability or incapacity, or is otherwise life-threatening in connection..." with the research study.

For this study, an SAE includes neonatal deaths such as still born babies or miscarriages or any life-threatening events that requires urgent medical attention, emergency care, and/or hospitalization due to early labor. A SAE can also be regarded as any undesirable experience associated with the use of a medical product in a patient or any life-threatening occurrence which could lead to disability / permanent damage, death or other serious medical events (including outcomes that may jeopardize a participant or which may require medical or surgical intervention). Participants in this study are individuals at risk for postpartum depression and other psychosocial issues, and are thus, as a population, at risk for clinical worsening. Although we do not believe the study procedures or intervention places clients at increased risk for clinical worsening, we will review and report events of clinical worsening that leads to hospitalization. These events are not anticipated to occur on a regular basis.

7.2. Identification and Initial Reporting of Incidents

The study depends upon staff to identify and report incidents promptly so that management can know about issues and respond appropriately. When study staff believe they have witnessed, experienced or learned of an event that fits the definition of an incident (AE or SAE), they should verbally report it immediately to the Project Coordinator. The staff member and the Project Coordinator will discuss the incident and if they agree it meets the definition of an incident, the Project Coordinator will provide guidance to the staff member, if needed, to complete, sign and submit the **Incident Report Form**.

In the case that an incident poses a threat to a staff member, the staff member should remove themselves from the threat according to safety procedures. If participants experience any adverse reactions to the intervention part of the study, the staff member will contact the Project Coordinator and/or Site PI immediately for additional support. Based on advice from senior project staff, the field staff will make recommendations for appropriate referrals to medical, counselling and/or other health services.

SAEs (e.g., death or hospitalization) will be reported within 24 - 48 hours of their occurrence by the Site PI, the PI, the SAMRC Research Ethics Committee, and our NIAAA project officer. SAEs will be reported regardless of whether they are considered to be study related. SAEs will be systematically assessed by staff at each participant contact as well as at each scheduled follow-up. At each follow-up, all research participants will be asked whether they had been hospitalized overnight in the past 30 days. In the event that a participant either withdraws from the study or the investigator decides to discontinue a participant due to an SAE, the participant will be monitored by the investigator via ongoing status assessment until (1) a resolution is reached (the problem requiring hospitalization has resolved or stabilized with no further changes expected), (2) the SAE is determined to be clearly unrelated to the study intervention, or (3) the SAE results in death. The PI will review the study protocol with other senior research staff and/or the ethics committee and determine what further action to take based on the best interests of the participants and of the research. With input from the PI, the SAMRC Research Ethics Committee may recommend continuation of the study, modifications to the study, or termination of the study if unacceptable.

Event	Description	Example	Reporting Requirements/Actions
Community/ Environmental Report	Any incident in which events in the community/study environment directly or indirectly have a time/cost/quality effect on the study progress. These incidents are either observed, reported in the media or information obtained from community members	Fires/Floods, natural disasters, taxi violence, service delivery strikes, development of RDP housing (temporary zone restructure resulting in community member migration), political activity, study team excluded from a community due to protest against the study	Reporting to: Project Coordinator Senior Management: PI & Site PI
Staff Safety Incident	Incidents in which staff or any other person are threatened	A participant or any other individual	Reporting to: Project Coordinator

		becomes violent towards a staff	Senior Management: PI & Site PI
Participant Harms			
Social Harm	
1) Any untoward social occurrences that happen to a participant as a result of their participation in the study, or
 
2) any untoward social occurrences that happen to a community, or groups or individuals within a community, as a result of implementation of the study intervention
	Participants provide confidential information and if this information is leaked it can have detrimental effects	
Reporting to: Project Coordinator Senior Management: PI & Site PI

Protocol Deviation	Protocol non-adherence/violations (the research project's processes not being followed) leading to individual incidents, trends or omissions that result in significant added risk to the participant, non-adherence to significant protocol requirements and significant non-adherence to GCP.	
-Enrollment of an ineligible patient.
 
-Informed consent not obtained prior to performing protocol-specified procedures.
 
-Protocol-specified procedures not followed.
 
-Breach of participant confidentiality
	
Reporting to: Project Coordinator Senior Management: PI & Site PI
 
All Co-Investigators SAMRC Research Ethics Committee NIH Project Officer

Critical Events			
Unanticipated Problems	Any incident, experience or outcomes that is unexpected, has reasonable possibility of being related to a subject's participation in the research and suggests that the research places participants or others at	
-Loss of a computer/tablet that contains participants' private identifiable information.
 
-Participant experiences physical violence (e.g., domestic) as a result
	
Reporting to: Project Coordinator Senior Management: PI & Site PI

	greater risk of harm than previously known or recognized.	of participating in a research study. -Unintentional disclosure of family member's or partner's health status due to participation in the research	
Suspected Research Misconduct	Suspected fabrication, falsification, or plagiarism in proposing, performing, or reviewing research, or in reporting research results.	-Study staff make up data to make it look like household visits were conducted that actually were not. -Staff falsify data on a questionnaire.	-Study staff will report allegations of research misconduct to the PI and/or designee within 24 hours of becoming aware of the incident. -In instances when the study staff cannot notify the PI and/or designee for fear of punishment or another reason, the study staff will notify an appropriate person within their institution. -The PI and/or designee will notify the appropriate person within the institution (e.g., SAMRC REC), and the funding representative, of all applicable known facts about the allegation.
Incidents Reportable to Civil Authorities	Incidents reportable to civil authorities include: Child abuse	Child abuse is observed during a household visit or whilst in the field

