3.5.2. Storing our data safely

Once we have collected the data, all the data should be stored safely.

The participant folders should be kept locked away in the filing cabinet, even if you are still busy at the clinic/healthcare facility. You should only have the folders out that you are busy with, and you should never go and have tea, or walk away, leaving any folders, supplies or valuables outside the cabinet. This also applies to any other forms or papers related to MaRISA. If you are not busy on the tablet, please also keep it in the locked cabinet and leave the tablet in the filing cabinet at the end of your shift.

Remember: Any hardcopy forms with patient names or contact details will be stored in the CONTACT folder. All other hardcopy forms will go into the EVERYDAY folder. Each of these files will be kept in separate drawers in the stainless-steel cabinets.

CHAPTER 5: STUDY PROCEDURES

4. Introduction and Expectations

Staff should keep in mind that they are patients' first contact with the project. In doing so, the team gives patients their first impression of the project.

How you approach people, your body language, dress code, attitude and what you say will leave a lasting impression on people who are screened for the study and others. These impressions can influence whether people will want to participate or not in the study. Be conscious of the impressions you make and be careful of what you say – try and make people feel comfortable and welcome.

For the pilot testing phase, we aim to recruit 60 (30 pregnant and 30 post-partum) women for the two healthcare facilities. Both the pregnant and post-partum women need to report that they are using alcohol. Fieldworkers will conduct the baseline assessment, 6-week follow-up assessment, and the 3month follow-up assessment.

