5.4. Follow-up Appointments and reimbursements

The participant will be reimbursed for their transport costs based on the following scale. Transport costs should only be reimbursed if the participant has needed to travel to come to the healthcare facility for a study appointment:

Categories of distances	Amount provided
0km – 3km	R10
4km – 10km	R30
11km +	R50

Pilot Phase:

In addition to monitoring participants' through urinalysis twice a week, participants will be asked to participate in the 6-week and 3-month follow-up assessments at the healthcare facility they were enrolled at.

A participant will be provided R150.00 each at baseline and follow-up assessments.

Consent will be obtained to collect participants' birthing facility information for those who were recruited during pregnancy to track birth outcomes. If a participant is already postpartum and breastfeeding, self-reported incidents of breastfeeding while using alcohol will be collected. Infants' data relating to their height, weight, and head circumference will be collected.

If a participant misses a visit, we will contact the participant following a standard protocol (i.e., phone call on the appointment day, the following day, and 1 week after the missed visit to encourage rescheduling for the missed appointment). Participant locator information will also be updated at each appointment. Staff members need to

prioritize tracking participants who have the least number of days left before their upcoming appointment so that they do not time out of the study. In other words, you should contact participants first whose next appointment is closest to the current date.

If a participant has withdrawn from the study or has reported the loss of her foetus/baby to field staff and this was reported to Project Coordinator, the participant should not be tracked any longer. These participants will also not be replaced in the study since they have been reported on.

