7.1.1. Adverse Events (AE)

Adverse Events (AEs) will be defined as: report of coercion to participate in the study; or significant hesitation, concern or emotional distress from answering research, such that the participant decides to stop their participation; and harm resulting from breach of confidentiality. Medical events for postpartum health, psychiatric issues including suicidal ideation, or substance abuse that do not require urgent medical attention, emergency care, and/or hospitalization will be also treated as AEs. We will monitor attrition rates for participants but drop out from the study will not be reported as an AE unless it is decided to be related to an untoward event from study participation. Clinically insignificant events are not considered AE's. Examples of clinically insignificant events include mild viral illness (e.g., colds, flu, and runny nose), common headaches, minor scratches, and mild symptoms or problems associated with medical conditions not related to the postpartum periods. As per the definition of AEs, only significant worsening of baseline medical or psychiatric status or new problems will be reported as AEs.

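### The protocol describes no scheduled question for adverse events or social harms, so their counts are probably too low and a low count should not be read as evidence of safety

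*Protocol*

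**What the plan says.** **Serious adverse events (SAEs).** Protocol section 7.2 states: "SAEs will be systematically assessed by staff at each participant contact as well as at each scheduled follow-up". It then gives one concrete question, put at each follow-up: "all research participants will be asked whether they had been hospitalized overnight in the past 30 days". How SAEs are assessed at the other contacts is not described.

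**AEs.** Section 7.1.1 counts reported pressure to take part, distress or concern that makes a woman stop, and harm from a confidentiality breach. It adds medical, psychiatric and substance-use events "that do not require urgent medical attention, emergency care, and/or hospitalization will be also treated as AEs".

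**Social harms.** The event table at the end of section 7.2 defines these, in its first limb, as "Any untoward social occurrences that happen to a participant as a result of their participation in the study". There is no hospital criterion.

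**Route for incidents.** Section 7.2 says: "The study depends upon staff to identify and report incidents promptly". Sections 7.1 and 7.2 start the process when a staff member becomes aware of an event, sees it, experiences it or learns of it.

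**Contacts.** Section 5.4 provides for assessments at 6 weeks and 3 months ("participants will be asked to participate in the 6-week and 3-month follow-up assessments") and for urine monitoring twice a week.

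**SAP.** It plans descriptive statistics and a trend test for change in alcohol use, violence and depression. It does not mention AEs, SAEs or social harms.

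**The concern.** The one specified question is aimed at events that most AEs and social harms, by their definitions, are not. For these the protocol describes no prompt, no look-back period and no record that a woman was asked and said no.

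The introduction to Chapter 7 lists coercion, disclosure of confidential information and social consequences of taking part as potential risks. Section 7.1 gives abuse by a husband because of participation as an example of a reportable incident. Such events mostly happen out of staff sight. Under section 2.2.2 the fieldworkers who screen, consent and enrol women also conduct the follow-up assessments, so a woman may be slow to raise pressure to take part without being asked.

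Two things are at stake. Help for a woman may be delayed, and the pilot's AE and social-harm counts would be biased toward zero without a clear denominator.

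**Working it through.** **1. Set the definitions beside the ascertainment.**

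| Harm | Defined in | Would the overnight-hospital question find it? |
|---|---|---|
| SAE with overnight admission | 7.1.2 | Yes, within the past 30 days |
| Medical, psychiatric or substance-use AE | 7.1.1 | No: defined as not needing hospital care |
| Pressure to take part | 7.1.1 | No: what counts is a report of it |
| Distress that makes a woman stop | 7.1.1 | No |
| Harm from a confidentiality breach | 7.1.1 | Only if it led to admission |
| Social harm | Table in 7.2 | Only if it led to admission |

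**2. Look for another scheduled source.**
- Section 5.3 lists violence exposure, stigma, and physical and mental health at baseline, and the SAP analyses change in violence and depression. These record status. Nothing described asks whether an event was due to the study or sends an answer to AE or social-harm review.
- The suicide-risk questions in 6.2.1 are used when a woman expresses intent, not on a schedule.
- The form for fetal, birth and neonatal outcomes (5.6.1) covers a different set of events.

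**3. Check the look-back of the question that exists.** Six weeks is 42 days. Taking 3 months as 91 days (an assumption), the second interval is 91 - 42 = 49 days. A 30-day look-back covers 30/42 = 71% of the first interval, 30/49 = 61% of the second, and 60/91 = 66% overall. About 31 days are missed unless SAEs are also asked about at the urine-monitoring contacts.

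**4. Illustrate the effect of incomplete capture.** There is no figure in the plan to reproduce: the documents give no harm rate, no capture rate and no derivation of the sample size beyond 30 + 30 = 60 (Chapter 5 introduction: "we aim to recruit 60 (30 pregnant and 30 post-partum) women for the two healthcare facilities"). Let p be the risk per woman and c the probability that a harm is recorded. Both are assumed, and all 60 women are taken as followed.

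Expected number of women with a recorded harm = 60 x p x c. P(none recorded) = (1 - p x c)^60.

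| p | c | Expected | P(none recorded) |
|---|---|---|---|
| 10% | 20% | 1.2 | 0.98^60 = 29.8% |
| 10% | 50% | 3.0 | 0.95^60 = 4.6% |
| 10% | 90% | 5.4 | 0.91^60 = 0.3% |
| 5% | 20% | 0.6 | 0.99^60 = 54.7% |
| 5% | 50% | 1.5 | 0.975^60 = 21.9% |
| 5% | 90% | 2.7 | 0.955^60 = 6.3% |

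Conversely, with zero recorded events the one-sided 95% upper bound on the true risk is [1 - 0.05^(1/60)]/c. This is 4.9% at c = 100%, 9.7% at c = 50% and 19.5% at c = 25%.

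**The case against.** Several stronger readings are tempting, and the documents do not support them.

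- **A reader might infer that these harms are counted only when a woman volunteers them.** That goes too far. Section 7.2 also covers what staff see or learn. Chapter 6 lists signs of distress to watch for. Section 7.1 makes breaches known to staff reportable, and section 7.1.1 monitors attrition. Chapter 4 has 20% of baseline and follow-up appointments observed remotely, with permission. Distress that ends participation would often be noticed.
- **A reader might infer that SAEs are found only through the hospitalization question.** Section 7.2 also requires assessment at each contact, and contacts are frequent ("In addition to monitoring participants' through urinalysis twice a week"). The method is simply not given.
- **A reader might infer that a finding of no harm would be worthless.** The SAP plans no such conclusion, and zero events still give a bound at any assumed capture rate.
- **A reader might infer that the study expects violence over participation.** Chapter 7 describes the study as minimal risk, and the event table gives such violence as an example of an unanticipated problem.

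Two further objections have weight. The follow-up assessments and the incident form are named but are not part of the published text, so they may already contain suitable items. And solicited AE collection in a minimal-risk pilot of 60 women is partly a design choice.

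These points limit the wording, but the gap remains. None supplies a scheduled AE or social-harm question, or a rule that links existing answers to study-relatedness or incident review.

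**Conclusion.** The concern holds in a limited form. In the text available, SAEs are the only harms with stated systematic ascertainment. AEs and social harms depend on a participant's report or on what staff notice or learn, so their counts are likely to be understated and a low count should not be taken as evidence of safety.

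The size of the shortfall cannot be estimated from the documents. The figures above show only how strongly the reading of a zero count depends on capture: the upper bound doubles from 4.9% to 9.7% if half of events are missed. They rest on assumed risks and capture rates and on complete follow-up of 60 women.

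This should be changed because the remedy is cheap and bears on participants' welfare. It does not undermine the planned analyses of alcohol use.

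**What to change.** In section 7.2, add a fixed yes/no set to the 6-week and 3-month assessments, covering the time since the last assessment:

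1. pressure to take part;
2. study information reaching other people;
3. threats or violence because of the study;
4. lasting distress from the questions;
5. any new or clearly worse health or mental-health problem.

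Have women complete it themselves on the tablet, in the CASI format that section 5.3 sets for baseline, so that they need not tell the person who enrolled them. Record no answers as well as yes answers, and send each yes into the existing incident route. Add a line to the SAP to report solicited and unsolicited events separately, with the number of women asked. That number matters because section 5.4 stops tracking women who withdraw or lose a pregnancy or baby, and the set would not reach them.

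If the follow-up forms already contain such items, it is enough to cite them in section 7.2 and link them to incident review.

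The cost is about five questions, or 2 to 3 minutes, at two visits already planned, plus a small REDCap form. The downside is more minor reports to triage.

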Maternal Alcohol Reduction Intervention in South Africa [MaRISA]

NCT05319977; May 18, 2021

Descriptive statistics will be used to describe the data for the overall sample and separately for participants enrolled while pregnant and postpartum. Data will be summarized using the mean (standard deviations) for continuous variables and percentages (frequency) for categorical variables. Changes from baseline to follow-up assessments on variables related to alcohol use and contextual/co-occurring issues (i.e., violence and depression) will be evaluated using the Cochran-Armitage Trend test. All analyses will be performed using SAS version 9.4.

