5.2. Screening

Once introductions are made and a patient's cooperation has been secured, complete the participant ID, staff ID, site and date fields on the screener, using the tablet.

- For the pilot phase, we will be using the "Pilot Screener for Pregnant and Post-Partum Women" at the onset of the pilot phase.

Recruitment will be done via clinic referrals, posters, and flyers.

Participant IDs will be according to the following format, it will consist of ten digits with both alphabetic and numerical items, e.g., M_BL0001PR or M_BL0001PP.

Please note: the first alphabetic digit refers to the MaRISA study, an underscore sign separates it from the next 2 alphabetic digits which indicates the site, e.g., Bishop Lavis = M_BL, the next 4 digits indicates how many participants have been enrolled into the study and the last 2 digits indicates whether the participant is currently pregnant or post-partum.

There are types of potentially sensitive information that are requested on the screening questionnaire. It is important to stress the confidential nature of the screener. Reassure them that their identity will never be linked to their responses and that their responses are only used for research purposes. Always remind individuals that their answers will be kept strictly confidential.

Staff ID#: Will be a staff member's Initials.

Site ID#: Bishop Lavis = M_BL; Macassar = 002

To be eligible, women must fulfil in the following criteria, i.e.:

Criterion	Participants
Age	Be ≥ 18
Pregnancy or Post-Partum Status	be pregnant (≤ 28 ges wks) or postpartum (≤ 3 mos)
Alcohol Use	
 have reported alcohol use during the current pregnancy or lactation test positive for alcohol use by urinalysis (i.e., EtG)
Birth Venue (linked to birth outcomes)	plan to complete antenatal care at the current clinic and remain in the area for at least 3 months
Cellphone Status	own a cell phone to receive text messages
Serious Medical Conditions and Suicidal Thoughts	women who report serious medical problems threatening their current pregnancy or report current suicidal thoughts or attempts in the past month are NOT eligible
Other	intend to breastfeed for 6 months

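### The SAP's only test of change, Cochran-Armitage, treats repeated assessments of the same women as independent groups, so for binary measures that vary at baseline its p-values are too large when within-woman correlation is positive

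*SAP*

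**What the plan says.** The SAP is a single analysis paragraph. It sets out descriptive summaries, overall and by enrolment status, and then one inferential method. The object of that method is "Changes from baseline to follow-up assessments on variables related to alcohol use" and the co-occurring issues, and the same sentence names the test: "variables related to alcohol use and contextual/co-occurring issues (i.e., violence and depression) will be evaluated using the Cochran-Armitage Trend test". Neither document names another test, a repeated-measures model or any adjustment for pairing. The paragraph expects variables of both types ("Data will be summarized using the mean (standard deviations) for continuous variables and percentages (frequency) for categorical variables") but does not say which of the tested variables are binary.

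The protocol shows who is compared. Chapter 5, Introduction and Expectations, says "we aim to recruit 60 (30 pregnant and 30 post-partum) women for the two healthcare facilities" and "Fieldworkers will conduct the baseline assessment, 6-week follow-up assessment, and the 3month follow-up assessment". Section 5.4 says "participants will be asked to participate in the 6-week and 3-month follow-up assessments at the healthcare facility they were enrolled at", and adds that women who withdraw or lose the pregnancy or baby are not replaced. The three time points are therefore one cohort, less any missed visits.

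Two further passages limit the point. The eligibility table in section 5.2 requires self-reported drinking in this pregnancy or while lactating, and also that women "test positive for alcohol use by urinalysis (i.e., EtG"). Section 5.4 also mentions monitoring "through urinalysis twice a week", which is separate from the scheduled assessments and is not considered here.

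No significance level, sidedness, power, expected rate, primary outcome or within-woman correlation is stated.

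**The concern.** Cochran-Armitage takes its variance from binomial sampling in separate groups. When the groups are the same women, part of each woman's response is shared across visits and cancels in the change. The test ignores that cancellation and judges the change against too much noise.

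At stake is the only planned test of whether violence, depression, or any drinking measure free to vary at baseline changed. In a 60-woman pilot, a real improvement could be read as no evidence of change when the same data, analysed within woman, would show it.

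**Working it through.** The plan gives no power or sample-size derivation, so there is no figure of its own to reproduce; 60 is a recruitment target.

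**Inputs.** From the documents: n = 60 and three assessments of the same women. Assumed: two-sided 5%, equal pairwise correlation rho between visits, visit scores 0, 1, 2, complete data unless stated, and illustrative rates.

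**Step 1, variance.** Let c_j be the centred scores and p_j the observed proportions. Under no change, with common rate p:

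- true variance of Σc_j·p_j = p(1−p)·Σc_j²·(1−rho)/n
- variance used by Cochran-Armitage = p(1−p)·Σc_j²/n

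The ratio is 1/(1−rho), so the test's Z is too small by a factor √(1−rho).

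**Step 2, size.** True size = 2·[1 − Φ(1.96/√(1−rho))]. Simulated values are for n = 60 and a 50% null rate.

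| rho | Formula | Simulated |
|---|---|---|
| 0.1 | 3.9% | 4.4% |
| 0.2 | 2.8% | 3.2% |
| 0.3 | 1.9% | 2.1% |
| 0.5 | 0.6% | 0.7% |

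In terms of a p-value, a correct 0.05 becomes 0.10 at rho 0.3 (Z = 1.96·√0.7 = 1.64) and 0.17 at rho 0.5 (Z = 1.96·√0.5 = 1.39).

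**Step 3, power for 60-50-40%.** By hand at rho 0.3: with equally spaced scores and complete data the trend contrast is 3 months minus baseline, here 0.20. Its true SE is √[(0.24 + 0.24)(1 − 0.3)/60] = 0.0748. Cochran-Armitage needs a difference of 1.96·√(2·0.25/60) = 0.179, so its power is Φ[(0.20 − 0.179)/0.0748] ≈ 61%. A within-woman test has Φ(0.20/0.0748 − 1.96) ≈ 76%. Simulation gives 63% and 75%. Simulated power in full:

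| rho | Cochran-Armitage | Within-woman trend | 3-month contrast, corrected GEE or mid-P McNemar |
|---|---|---|---|
| 0.1 | 61% | 64% | 61% |
| 0.2 | 62% | 70% | 67% |
| 0.3 | 63% | 75% | 73% |
| 0.5 | 65% | 89% | 88% |

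The within-woman trend test is a one-sample t test on each woman's linear contrast. Its own simulated size is about 4.5% to 5.7%, so part of its small lead at rho 0.1 may come from that. At rho = 0 it has 59% against 61% for Cochran-Armitage.

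For 30-22.5-15% at rho 0.1, 0.3 and 0.5, Cochran-Armitage has 50%, 50% and 51%, against 55%, 65% and 80% for the within-woman trend.

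**Step 4, one data set, four pairings.** Take 30/60 falling to 20/60. Cochran-Armitage uses the pooled rate 50/120 = 0.417: Z = −0.1667/√(0.417·0.583·2/60) = −1.85, p = 0.064, whatever the pairing. The within-woman result depends on who changed:

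| Stop / start | rho | Exact McNemar p | Mid-P | Paired Wald 95% CI, points |
|---|---|---|---|---|
| 13 / 3 | 0.49 | 0.021 | 0.013 | 4.3 to 29.0 |
| 15 / 5 | 0.35 | 0.041 | 0.027 | 2.7 to 30.7 |
| 18 / 8 | 0.14 | 0.076 | 0.052 | 0.6 to 32.8 |
| 20 / 10 | 0 | 0.099 | 0.071 | −0.7 to 34.1 |

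The estimated change is 16.7 points in every row. Only the evidence attached to it differs.

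**The case against.** The best case for leaving the plan alone is that this is a small, mainly descriptive pilot, the error is conservative, no stated decision hangs on these p-values, and every magnitude above is assumed. Much of that stands. The SAP states no 5% rule, rho is unknown, and a negative rho would reverse the direction. But the sponsor chose to test change, and the chosen test's error rate drifts with a correlation nobody has specified.

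A second objection concerns the remedy and also stands. A reader might infer that any paired analysis would do better. Testing both follow-ups against baseline by mid-P McNemar, uncorrected, gives about an 8.2% to 8.3% chance of at least one false positive under a 50% null. With Bonferroni (0.025 each), 3-month power for 60-50-40% is 51.5%, 56.1%, 62.9% and 81.3% at rho 0.1, 0.2, 0.3 and 0.5, against 61.3%, 61.7%, 63.1% and 65.0% for Cochran-Armitage. Two corrected contrasts therefore lose at 0.1 to 0.2, roughly tie at 0.3 and gain only at 0.5. The advantage belongs to a single within-woman test.

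Third, a reader might infer that all the drinking results are affected. The documents do not support that. Section 5.2 requires both reported drinking and a positive EtG, so EtG at entry, or yes/no use over the eligibility window, is 100% at baseline and has no correlation with follow-up. The documents identify no dichotomised drinking measure that does vary at baseline.

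**Conclusion.** The point holds for binary variables that vary at baseline: violence, depression if dichotomised, and any drinking measure not fixed by eligibility. The independence assumption fails by design, and under positive rho the test is conservative. On the assumptions above, the loss of power is small at rho 0.1 (about 3 percentage points for 60-50-40%), material at 0.3 (about 12) and large at 0.5 (about 24). Missed visits weaken the effect without removing it.

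A reader might infer inflated false positives, since ignored correlation often has that effect. Here the comparison is within woman, so positive correlation works the other way. Nor are the observed proportions or their changes wrong; only the p-values are. Separately, Cochran-Armitage does not fit any tested variable kept on a continuous scale. This should be fixed before analysis, but it does not undermine the data collection.

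**What to change.** Replace Cochran-Armitage with one pre-stated within-woman test per outcome, and state alpha and sidedness.

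- **Binary outcomes that vary at baseline:** a single linear trend over visits from a repeated-measures logistic model (GEE with small-sample correction) on all available visits. Alternatively, name 3 months versus baseline as the single test, by GEE or mid-P McNemar. Report the 6-week change as an estimate with 95% CI only. If both contrasts are tested, state the multiplicity correction.
- **Continuous outcomes:** a linear mixed model with the same single contrast.
- **Measures at 100% at baseline by eligibility:** the follow-up proportion with an exact CI, for example 45/60 = 75%, 95% CI 62% to 85%.

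The cost is SAP wording and minor SAS 9.4 programming, with no new data, visits or participants. There are statistical costs too. McNemar drops women who miss a visit. Mid-P McNemar has slightly less power than Cochran-Armitage at rho = 0 (57% against 61%). With 20% random loss by 3 months it is also lower at rho 0.1 (52% against 55%), where GEE on all available visits matches Cochran-Armitage at 55%. With the same loss at rho 0.3 and 0.5, GEE has 65% and 82% against 54% and 58%, which favours GEE if missed visits are expected.
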